#### **5.6.B. Data Collection Strategy § 5.1.H.**

#### **5.6.C. Data Analysis**

Specific Aim 1: H1 Analysis (Summative Evaluation). We will first calculate descriptive statistics such as frequencies, proportions, means, and standard deviations for reach, adoption, and implementation measures for the overall sample (i.e., VISN 12 and Houston) and for each specific facility. We will determine cost-utilization of resources within both study arms and the incremental cost-effectiveness ratio (ICER), which is the difference in the estimated mean cost between the intervention and control groups divided by the difference in the estimated mean effectiveness between the two study arms. The base-case will be the control group. We will estimate two ICERs: 1) the incremental cost per additional number of study patients with clinically significant HbA1C reductions, and 2) the incremental cost per additional quality adjusted life-year gained, of the intervention arm over the study period respectively. We will calculate ICER as a ratio of the difference in the estimated mean total cost between the EPIC and EUC groups divided by the difference in the estimated mean number of patients whose HbA1c levels are significantly improved between the two study arms. Similarly, we will calculate ICER of the intervention in terms of the quality adjusted life-year as a ratio of the difference in the estimated mean total cost between the intervention and control groups divided by the difference in the estimated mean total number of quality adjusted life-year between the two study arms. We will use a commonly used threshold, \$50,000 per quality adjusted life-year gained, as a reference point to determine if the intervention is cost effective.

Because cost data are typically right-skewed and also subject to bias due to death and/or attrition, we will directly model the logarithm of costs using generalized linear modeling with a logarithmic link function and inverse probability weight to adjust for these potential biases. We will control any baseline imbalance between groups with respect to the cluster and study population characteristics in the calculations of expected mean cost and effectiveness. The estimated value of cost and quality adjusted life-year will not be discounted given a relatively short follow-up period in the study.

We will conduct exploratory analyses to examine associations between implementation measures (RE-AIM elements in table 5) and study outcomes following the conclusion of Phase 2. For example, for all eligible patients, within each PACT demographic characteristics will be compared between enrolled and non-enrolled patients using chi-square tests and independent samples t-tests. Fisher's Exact Test and the Wilcoxon Mann-Whitney tests will be used where appropriate. An index of reach representativeness will be calculated for each PACT which will then be correlated with post-intervention outcomes, controlling for respective baseline values. Similarly, for all PACTs sampled, PACT characteristics (e.g., panel size) will be compared between sampled and non-sampled PACTs using chi-square tests and independent samples t-tests. An index of adoption representativeness will be calculated for each PACT which will then be correlated with post-intervention outcomes, controlling for respective baseline values. Additionally, for patients receiving the EPIC intervention within each PACT, post-intervention HbA1c will be separately regressed on 1) the proportion of group sessions attended, 2) the proportion of individual sessions attended, and 3) baseline objective ratings of the group leader's fidelity. These models will control for baseline HbA1c and will be conducted using ANCOVA methods. Predictors that are significant at  $p < 0.25$  will be included in a multiple linear regression to examine both collective and unique predictors of post-intervention HbA1c levels (once again controlling for baseline HbA1c). Similar univariate and multivariate models will be formed to predict post-intervention DDS.

Specific Aim 2: The distributional nature of all variables will be assessed, and nonparametric tests (e.g., Fisher's Exact Test; Mann-Whitney test), data transformations (e.g., log linear), or other alternate methods (e.g., weighted least squares regressions) will be conducted where appropriate. First, we will compare baseline demographic, clinical, and patient-centered variables (including medication use) between EPIC and EUC with chi-square and independent samples t-tests. Variables with p-values  $< 0.25$  will be included as control variables or propensity scores in subsequent models. We will then compare baseline demographic, clinical, and patient-centered variables between those who complete the study and those who do not using chi-square and independent samples t-tests. Outcome analyses at both post-intervention and post-maintenance will be intention-to-treat and will use the multiple imputation procedures Proc MI and MINANALYZE in SAS Version 9.3 to estimate missing observations. We will evaluate the degree of dependency between patients within a given group session, between patients in a given PACT, and between PACTs within each of the five sites (by examining Intra Class Coefficients). It is likely that significant dependency will exist, and if so, we will accordingly take these into account in analyses (i.e., patients will be nested within PACTs which will in turn be nested within sites). Random regression methods using SAS Proc Mixed will be employed to account for clustering of data.

5.6.C.i. H2 Analyses (Effectiveness) We will employ Analysis of Covariance (ANCOVA) to examine treatment differences in outcomes immediately post-intervention (at 4 months). We will conduct two models: one with HbA1c at post-intervention as the outcome and one with DDS at post-intervention as the outcome. Models will include treatment group (i.e., EPIC versus EUC) as a predictor and respective HbA1c and DDS baseline scores and any demographic,

clinical, or patient-centered variables that differed between the study arms at baseline as covariates. We will calculate treatment effect sizes immediately post-intervention.

5.6.C.ii. H3 Analyses (Maintenance) Analyses for examination of maintenance of treatment effects will be similar to those for immediate treatment effects post-intervention. We will again employ ANCOVA to examine treatment differences in outcomes at the post-maintenance (10-month) assessment. We will conduct two models: one with HbA1c at 10-months as the outcome and one with DDS at 10-months as the outcome. Models will include treatment group (EPIC versus EUC) as a predictor and respective HbA1c and DDS post-intervention scores and any demographic, clinical, or patient-centered variables that differed between the study arms at baseline as covariates. We will calculate treatment effect sizes at the 10-month assessment.

5.6.C.iii. Exploratory Analyses (Implementation and Effectiveness) We will use a mixed-model approach to conduct separate repeated-measures analyses for HbA1c and DDS simultaneously using all three assessment time points. We will employ growth curve analyses using SAS Proc Mixed to examine overall group differences in improvements or decrements in outcomes over the year, maximize participant data, and account for dependency between patients within a given group session, PACT, and site. Conditional models will contain fixed terms for the intercept, treatment (EPIC or EUC), assessment time period, treatment by time period interaction, and previously identified variables that differ between treatment groups. Modeled random effects will include between-patient variation in baseline scores (i.e., the intercept where baseline assessments are scored 0) and variation in the slopes for time. With three assessments, the focus will initially be on linear patterns of change, although we will evaluate the relative fit of a quadratic pattern of change using the likelihood ratio test. These analyses will allow us to examine the immediate impact of treatment at post-intervention as well as retention, improvement, or decay in outcomes post-maintenance period. The treatment effect will assess differences between the two groups at baseline, the fixed effect of time will measure the average change over time in the outcome (collapsing across the two treatment groups), and the time by treatment interaction will indicate whether change over time (in slopes) differs between EPIC and EUC.

Several variables will be examined as separate mediators of the relationship between intervention group (EPIC versus EUC) and post-intervention outcome variables: 1) patients' perceptions of goal-setting engagement by the designated PACT member (CSQ), 2) objective ratings of goal and action plan quality (GET-D), 3) self-efficacy for diabetes self-management, 4) diabetes self-management adherence, and 5) mediation adherence. For each mediator, we will conduct three separate models to test for mediation between intervention group and each outcome: 1) the first model will regress post-intervention HbA1c levels on treatment group and baseline HbA1c levels, 2) the second model will regress the mediator on treatment group and baseline HbA1c levels, 3) the third model will regress post-intervention HbA1c levels on treatment group, baseline HbA1c levels, and the mediator. Parallel analyses will be conducted to predict change in DDS. We will use bootstrapping methods to calculate the unstandardized estimate of the indirect effects as well as unbiased confidence intervals. Significance will be established if the 95% confidence interval of the indirect effect does not include zero. Bootstrapped analyses will be performed using MPlus Version 6.

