comprehensive cost-based database system. We will use a micro-costing approach to track and record all expenses related to the EPIC and EUC components and non-research related resource consumptions such as the educational materials and staff time spent on both study arms. We will retrieve medical utilization and cost data from the National Patient Care Database and the Decision Support System. We have experience working with each of these data sources in our prior HSR&D funded work. The National Patient Care Database includes outpatient and inpatient clinical, demographic, and utilization data (e.g., patient age, race, diagnosis and procedure codes, clinic location where care is provided, and the provider of care). The Decision Support System, a managerial cost accounting system, produces National Data Extracts that provide cost and utilization information for a range of health care activities, including laboratory, pharmacy, radiology, outpatient services, and inpatient treating specialty units. Unit cost of personnel time will be based upon the actual salary rate and fringe. Unit cost of other resources such as supplies and facilities will be derived from the VA accounting system. Total costs for each patient will be the summed products of quantities of resources used multiplied by the unit cost for those resources. All costs will be adjusted to constant US dollars in 2016. For cost-effectiveness, we will use two measures: 1) number of study patients with clinically significant improvements in HbA1c; and 2) number of quality adjusted life-years using the validated EQ-5D instrument to derive health utility weights. The utility score (weight) of each individual patient at each observational interval over the trial period (baseline to 4 months to 10 months) will be calculated according to the scoring algorithms provided by the EQ-5D developers. The primary end-point measures of cost-effectiveness are: 1) the incremental cost per additional number of study patients whose HbA1C are significantly improved and 2) the incremental cost per additional quality adjusted life-year gained, of the intervention relative to the control group.

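### The $50,000-per-QALY determination rests on a point-estimate ICER, and no sampling uncertainty is planned for either cost-effectiveness ratio

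*Combined protocol and SAP*

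**What the plan says.** Section 5.6.C (Specific Aim 1, H1 analysis) defines the ICER as a ratio of two contrasts between EPIC and EUC: "difference in the estimated mean cost between the intervention and control groups divided by the difference in the estimated mean effectiveness between the two study". Two are planned: cost per additional patient with a clinically significant HbA1c reduction, and cost per QALY gained. For the second, the plan takes $50,000 per QALY "as a reference point to determine if the intervention is cost effective".

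These are not incidental summaries. The text following Table 5 in section 5.5.A.i introduces them with "The primary end-point measures of cost-effectiveness are", and the second is "the incremental cost per additional quality adjusted life-year gained, of the intervention relative to the control group". Utilities come from the EQ-5D "over the trial period (baseline to 4 months to 10 months").

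The nearby statistical provisions are these:
- For costs, "we will directly model the logarithm of costs using generalized linear modeling with a logarithmic link function and inverse probability weight". The stated purpose is to deal with skewness and with bias from death or attrition.
- For both cost and effectiveness, "We will control any baseline imbalance between groups with respect to the cluster and study population characteristics".
- Section 5.1.H.iii plans sensitivity analyses, but for missing data.
- Section 5.6.C.iii plans bootstrap confidence intervals, but for mediation effects.

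I found no confidence interval, bootstrap, Fieller interval, net-benefit analysis or acceptability curve for either ICER.

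**The concern.** A verdict of cost effective or not would be read off a single ratio of two estimated differences, with nothing to show how far chance could have moved it. Two things make this worse than an ordinary missing interval.

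First, the denominator is a QALY difference over ten months. When it is close to zero, small changes in it move the ratio by large amounts or change its sign.

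Second, the value of the ratio does not identify the conclusion. A negative ICER arises both when EPIC saves money and adds QALYs (it dominates) and when it costs more and loses QALYs (it is dominated). The plan does not say how the two are to be told apart.

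At stake is the conclusion on the plan's own primary measures of cost-effectiveness, which also form part of H1.

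**Working it through.** **1. The plan's own figure.** The documents give no precision or power figure for costs or QALYs, so the sample size in section 5.6.A sets the precision. For d = 0.40, 80% power and two-sided alpha 0.05: n = 2(1.960 + 0.842)²/0.40² = 98.1, so 99 per arm (stated: 100). Deff = 1 + 11 × 0.0183 = 1.2013, and 100 × 1.2013 = 120. Then 120/0.85 = 141.2, so 142 per arm. The stated 142 reproduces.

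**2. The sign problem (no assumed numbers).** Write ΔC and ΔQ for the estimated cost and QALY differences, and INMB = 50,000 × ΔQ − ΔC. If ΔQ > 0, then ΔC/ΔQ < 50,000 is equivalent to INMB > 0, as intended. If ΔQ < 0, multiplying through reverses the inequality, so ΔC/ΔQ < 50,000 is equivalent to INMB < 0. Whenever the estimated QALY difference is negative, the literal comparison returns the opposite of the right answer.

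**3. Precision of the QALY difference (assumed SDs).** Trapezoid weights for visits at 0, 4 and 10 months are 0.167, 0.417 and 0.250 years (total 0.833). Assumptions: common utility SD s, equal correlation ρ between visits, 120 completers per arm and Deff 1.2013. The documents give neither s nor ρ, and they do not say for which outcome the ICC of 0.0183 was found.

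- Unadjusted QALY variance = s²(0.2639 + 0.4306ρ).
- Variance adjusted for baseline utility = s²[0.2361(1 − ρ²) + 0.2083(ρ − ρ²)].
- 95% half-width = 1.96 × √(2 × 1.2013/120) × SD of QALY = 0.277 × SD of QALY.

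| s | ρ | Half-width, adjusted | Half-width, unadjusted |
|---|---|---|---|
| 0.10 | 0.5 | 0.0133 | 0.0192 |
| 0.10 | 0.8 | 0.0095 | 0.0216 |
| 0.15 | 0.7 | 0.0169 | 0.0313 |
| 0.20 | 0.7 | 0.0225 | 0.0417 |
| 0.25 | 0.5 | 0.0332 | 0.0480 |
| 0.25 | 0.8 | 0.0239 | 0.0541 |

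Multiplied by $50,000, the adjusted range is about $480-$1,660 and the unadjusted range about $960-$2,700 per patient, before any cost variance. With all 142 per arm and no design effect, the multiplier falls from 0.277 to 0.233, so the half-widths are about 16% smaller.

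**4. Against possible gains.** A constant utility gain g at 4 and 10 months gives g × (0.417 + 0.250) = 0.667g QALY: 0.007 for g = 0.01, 0.013 for 0.02, 0.020 for 0.03 and 0.033 for 0.05. With s = 0.15-0.20 and ρ = 0.7, the half-width exceeds the gain when g is below about 0.025-0.034 (adjusted) or 0.047-0.063 (unadjusted). A utility effect of d = 0.40 would give 0.667 × 0.40s = 0.267s QALY. That is above the largest unadjusted half-width, 0.277 × 0.780s = 0.216s, at every s.

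**5. What a point-estimate rule does (illustration).** Assume s = 0.20, ρ = 0.7, baseline adjustment, true incremental cost $500, cost SD $5,000, and cost and QALY errors independent. The SE of ΔQ is 0.0810 × 0.1415 = 0.01146, worth $573. The SE of ΔC is 5,000 × 0.1415 = $707. The SE of INMB is √(573² + 707²), about $911. Even if the sign problem is avoided by using the sign of the estimated INMB:
- True gain zero: INMB = −$500, and the estimate is positive with probability Φ(−500/911) = 29%.
- True gain 0.020 QALY (true ICER $25,000): INMB = +$500, and the estimate is negative 29% of the time.

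The estimated QALY difference is zero or negative, where step 2 applies, 50% of the time at zero true gain, 27% at 0.007, 12% at 0.013 and 4% at 0.020.

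**The case against.** A fair defence has four parts.

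- **Wording and weight.** The plan speaks of a reference point. This is a hybrid type 1 trial focused on effectiveness (section 2.B), and no sample size or effectiveness conclusion depends on the ICER. This limits the consequence. The sentence nonetheless goes on to a determination, and no other decision rule is given.
- **Size of the noise.** A reader might infer that QALY noise is bound to exceed any plausible gain. The documents do not support that. They give no EQ-5D SD and no expected gain, and a utility effect of d = 0.40 would exceed the half-width at every SD considered. That d was set for HbA1c and DDS, so it does not show that such a utility gain is expected. It does show that the blanket statement fails.
- **Adjustment.** Baseline imbalance is to be controlled, and EQ-5D is measured at baseline. If baseline utility is a covariate, the half-width at ρ = 0.7 is only slightly more than half the unadjusted one. The plan does not name it as a covariate, so both cases are shown.
- **Scope.** The threshold applies only to the QALY ICER. Nothing here shows that the HbA1c-responder ICER is unstable; its denominator derives from an outcome used to size the trial. For that ratio, only the missing interval stands.

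It is also true that any reported uncertainty measure would fill the bare omission. Net benefit is preferred because it also removes the sign problem.

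**Conclusion.** The point holds. The cost-effectiveness determination compares a point-estimate QALY ICER with $50,000, and neither ICER has a planned measure of sampling uncertainty. The reversal for negative QALY differences follows from algebra and needs no assumption.

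The size is conditional on utility SD 0.10-0.25, correlation 0.5-0.8, 120 completers per arm and Deff 1.2013. Under these, the 95% half-width is about 0.010-0.033 QALY adjusted or 0.019-0.054 unadjusted, roughly $480-$2,700 per patient before cost variation. The 29% error rates belong to one illustrative set of inputs and are not a forecast. The conclusion is that noise may exceed a small gain, not that it exceeds every gain. This is a worthwhile improvement to a secondary part of the trial; the HbA1c and DDS comparisons are unaffected.

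**What to change.** In section 5.6.C, base the $50,000 determination on incremental net monetary benefit, 50,000 × ΔQ − ΔC, with a 95% bootstrap interval. Specify that:
- QALYs are adjusted for baseline EQ-5D;
- resampling respects both the EPIC group and the PACT clustering;
- the inverse probability weights and the cost model are refitted in each resample;
- an interval that includes zero is reported as uncertain.

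Report an interval for the HbA1c-responder result as well, and present both ICER point estimates alongside, stating the signs of the cost and effect differences. An acceptability curve is optional.

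The change uses cost and EQ-5D data already being collected and does not affect recruitment or procedures. It costs a little more analysis, and the cost-effectiveness conclusion may turn out to be uncertain. It should be fixed before outcome data are examined.

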HbA1c levels	X	X	X	X	Diet/Exercise	X	X	X
Diabetes Distress Scale		X	X	X	Pharmacy refills (database)	X	X	X
Baseline Covariates					Goal-Setting Evaluation Tool	X	X	X
Patient Activation Measure		X	X	X	Attendance in group visits		X	X
Functional Health Literacy measure		X			Post-intervention Implementation variables			
The Spoken Knowledge in Low Literacy in Diabetes (SKILLD) Knowledge Assessment Scale		X			Patient exit interviews (Attachment 7)		X	
Patient Socio-demographics		X			Clinician exit interviews (Attachment 13)			X
Baseline clinical characteristics		X			Summative implementation variables			
PACT and facility characteristics		X			Reach and Adoption measures	X	X	X
Patient knowledge & understanding of DM					Fidelity measures	X	X	X
EQ-5D		X	X	X				
		X	X	X				

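### The QALY comparison does not commit to including baseline EQ-5D utility; covariate control depends on observed imbalance in characteristics that are not defined

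*Combined protocol and SAP*

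**What the plan says.** Section 5.5.A.i takes "quality adjusted life-years using the validated EQ-5D instrument to derive health utility weights", with utilities scored "at each observational interval over the trial period (baseline to 4 months to 10 months"). Table 10 schedules EQ-5D at all three visits. The text does not say how the three utilities are combined into a QALY.

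Section 5.6.C (Aim 1, H1 analysis) plans two ICERs. One is per additional patient with a clinically significant HbA1c reduction. The other is "the incremental cost per additional quality adjusted life-year gained, of the intervention arm over the study period respectively". A figure of $50,000 "per quality adjusted life-year gained, as a reference point to determine if the intervention is cost effective". Section 5.5.A.i counts both ratios as primary end-points of the cost-effectiveness work.

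The only covariate rule stated for this analysis is "We will control any baseline imbalance between groups with respect to the cluster and study population characteristics", applied to expected mean cost and effectiveness. The characteristics are not listed, and the size of imbalance that triggers control is not given.

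The H2 models in 5.6.C.i are specified differently. They include the baseline value of the outcome (HbA1c or DDS) in every case, and then add any variables that differ between arms.

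**The concern.** Under an area-under-the-curve calculation, baseline utility is part of the QALY itself, and it also predicts the two later utilities. A chance difference between arms at baseline therefore passes into the QALY difference unless the model removes it. A rule that acts only on observed imbalance may or may not remove it, depending on what counts as a characteristic and what counts as imbalance. Both would be decided after the data are seen.

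QALY differences over 10 months may be small, and the ICER divides by them, so a modest shift in the denominator can move the ratio a long way relative to a fixed reference point.

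**Working it through.** **Inputs from the documents.** d = 0.40, two-sided alpha 0.05, 80% power, ICC 0.0183, 12 patients per PACT, 15% attrition, 142 per arm (5.6.A); utility times 0, 4 and 10 months (5.5.A.i); $50,000 per QALY (5.6.C).

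**Assumptions, not in the documents.** EQ-5D SD 0.20 (range 0.15 to 0.25); equal correlation ρ between visits of 0.4, 0.6 or 0.8; trapezoid area for the QALY; clustering and attrition ignored.

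**1. Arm size.** The two-sample formula gives 2(1.960 + 0.842)²/0.40² = 98.1, so 99 per arm (the plan states 100). Design effect 1 + 11 × 0.0183 = 1.2013, giving 120. Then 120/0.85 = 141.2, so 142 per arm and 284 in total. The plan's figure reproduces. The documents give no QALY standard error or ICER to reproduce.

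**2. QALY weights.** The trapezoid over 0–4 and 4–10 months gives 2/12 for baseline, 5/12 for month 4 and 3/12 for month 10, summing to 10/12. Baseline has 2/10 = 20% of the weight.

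**3. Standard error of the QALY difference.** With V = Σw²(1 − ρ) + ρ(Σw)² = 0.2639(1 − ρ) + 0.6944ρ and slope b = 2/12 + ρ × 8/12:
- unadjusted SE = 0.20 × √(2V/142)
- SE adjusted for baseline = 0.20 × √(2(V − b²)/142)
- the intermediate case, adjusting only when the baseline p < 0.25, was simulated with 400,000 draws of the arm differences.

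| ρ | b | No adjustment | Only if p < 0.25 | Always adjusted |
|---|---|---|---|---|
| 0.4 | 0.433 | 0.0157 | 0.0130 | 0.0118 |
| 0.6 | 0.567 | 0.0172 | 0.0128 | 0.0106 |
| 0.8 | 0.700 | 0.0185 | 0.0120 | 0.0082 |

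Compared with no adjustment, always adjusting removes 43%, 61% and 81% of the variance (b²/V). Compared with the p < 0.25 rule it removes 1 − (0.0118/0.0130)² = 18%, then 31% and 53%.

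**4. Shift from a chance imbalance.** One SE of the baseline difference is 0.20 × √(2/142) = 0.0237. Its direct contribution is 0.0237 × 2/12 = 0.004 QALY. With carry-over it is b × 0.0237 = 0.0103, 0.0135 and 0.0166 QALY. At $50,000 per QALY, that is about $510 to $830 per patient. Over SD 0.15 to 0.25 and the same correlations, the shift is 0.008 to 0.021 QALY. An imbalance just short of p = 0.25 (1.15 SE) would leave 0.012 to 0.019 QALY uncorrected at SD 0.20.

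**5. Illustration on the ICER.** Assume a utility gain of 0.03 at both follow-ups and a cost difference of $800. The QALY gain is 0.03 × 8/12 = 0.020 and the ICER is $40,000. At ρ = 0.6, a one-SE imbalance gives 800/(0.020 + 0.0135), about $24,000, or 800/(0.020 − 0.0135), about $122,000. With an assumed gain of 0.05 the QALY gain is 0.0333 and the ICER is $24,000; the adverse imbalance then gives 800/(0.0333 − 0.0135), about $40,000, and the reference point is not crossed.

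**The case against.** A reader might infer that the plan excludes baseline EQ-5D. The documents do not say that. The control rule covers cluster and study population characteristics and extends to effectiveness, and the second term is undefined. As far as its layout can be read, Table 10 lists EQ-5D below the heading "Baseline Covariates". Section 5.6.A says in general terms that models will be adjusted for baseline covariates. The Aim 2 text in 5.6.C screens patient-centred variables at p < 0.25. The plan is under-specified, and the analyst could legitimately adjust. None of these texts commits to it, however: Table 10 is a collection schedule, 5.6.A names no covariate, and the p < 0.25 screen sits under a different aim and is itself conditional.

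The benefit also depends on the comparator. If EQ-5D did fall under the p < 0.25 rule, the larger imbalances would be corrected and the further variance saving would be 18% to 53%, not 43% to 81%. That stands, and both comparisons are shown for this reason.

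A reader might also infer that baseline differences bias the result or determine the ICER. Patients are individually randomised, so such differences average to zero over repetitions; what remains is lost precision and bias conditional on the imbalance that occurred. The documents give no EQ-5D SD, correlation, QALY gain or cost difference, so no effect on this trial's ICER can be demonstrated, and the $40,000 example was placed near the reference point by choice.

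Finally, this is a hybrid type 1 trial focused primarily on effectiveness, with cost-effectiveness one of several implementation measures. That limits the weight of the point.

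**Conclusion.** The point holds as a gap in specification with a clearly better and nearly free alternative. Control in the QALY comparison depends on observed imbalance, and baseline EQ-5D is not a committed covariate, although it is already collected and the H2 models treat their own baselines as fixed terms. The consequence is confined to the QALY ICER.

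The sizes rest on the assumed trapezoid formula, SD and correlations. Under them, routine adjustment is the most precise of the three options at every correlation examined, and a one-SE imbalance left unadjusted is about half to most of an assumed 0.020 QALY gain (0.0103/0.020 = 52% to 0.0166/0.020 = 83%). Whether that would change the cost-effectiveness conclusion depends on the true gain and cost difference, which the documents do not give.

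**What to change.** In 5.6.C, under the Aim 1 analysis, state how the utilities at baseline, 4 and 10 months are combined into each patient's QALY. Then estimate the QALY difference by regressing that QALY on arm and baseline EQ-5D utility, with baseline utility always in the model whatever imbalance is observed. The existing imbalance rule can remain for other characteristics, provided they are listed and the trigger is defined.

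This costs two sentences and one covariate. It needs no new data, visits or patients.

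Adding each patient's pre-randomisation VA cost to the cost model is an optional extension. It assumes that such costs can be drawn from the databases named in 5.5.A.i, which state no pre-randomisation extraction period, and its benefit has not been quantified here.
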